1.4 Schedule of Spirometry and In-Clinic Dosing with Blinded Study Medication

Table 4: Schedule of Spirometry and In-Clinic Dosing with Blinded Study Medication

Every effort should be made to initiate spirometry according to these timings:	Visit 1 Randomization	Week 6 Visit 2	Week 12 Visit 3	Week 24 Visit 5	Early Term/Withdrawal
Pre-Dose Spirometry	Two separate timepoints within 40 minutes prior to dosing.	Within 40 minutes prior to dosing AND between 11.5 and 12 hours after the patients evening dose the day prior to this visit.	Within 40 minutes prior to dosing AND between 11.5 and 12 hours after the patients evening dose the day prior to this visit.	Within 40 minutes prior to dosing AND between 11.5 and 12 hours after the patients evening dose the day prior to this visit.	Within 40 minutes prior to dosing AND between 11.5 and 12 hours after the patients evening dose the day prior to this visit (if applicable).
Morning Blinded Study Medication Dosing in the Clinic	Time: Between 6 AM and 10 AM	Time: Between 6 AM and 10 AM	Time: Between 6 AM and 10 AM	Time: Between 6 AM and 10 AM	Time: Between 6 AM and 10 AM
Post-Dose Serial Spirometry	30 min, 1, 2, and 4 hours post-dose.	30 min, 1, 2, and 4 hours post-dose.	30 min, 1, 2, 4, 6, 8 hours and the 12 hour post-dose spirometry should not start prior to 11.5 hours.	30 min, 1, 2, and 4 hours post-dose.	30 min, 1, 2, 4, 6, 8 hours and the 12 hour post-dose spirometry should not start prior to 11.5 hours.
Evening Blinded Study Medication Dosing ¹	None	None	Time: After completion of the 12-hour spirometry and between 6 PM and 10 PM	None	None

Note: Additional details on information contained in this table can be found in Section 6.0 and Section 8.3.1. For pre-dose spirometry conducted between 11.5 and 12 hours after the patients evening dose the day prior to the visit, the paper diary with the evening dosing completion time should be consulted.

¹Patients may be discharged from the clinic after Week 12 assessments are complete to self-administer their evening dose of study medication. If administered in the clinic, the Week 12 evening dose must be administered by unblinded site staff.

2.0 INTRODUCTION

2.1 Study Rationale

Verona Pharma plc. is developing inhaled nebulized ensifentrine for the maintenance treatment of chronic obstructive pulmonary disease (COPD). RPL554-CO-301 is one of the two Phase III confirmatory studies for the inhaled nebulized ensifentrine suspension formulation in patients with COPD.

The two confirmatory studies RPL554-CO-301 and RPL554-CO-302 are planned as randomized, double-blind, parallel-group, placebo-controlled studies intended to provide replicate evidence of efficacy in terms of improvements in lung function, symptoms and quality of life and the safety of ensifentrine compared to placebo in patients with moderate to severe COPD.

RPL554-CO-301 will enroll approximately 800 patients with moderate to severe COPD in 2 subsets. The 24-week subset will enroll approximately 400 patients randomized 1:1 ensifentrine (3 mg): placebo and the 48-week subset will enroll approximately 400 patients randomized 3:1 in order to minimize the number of patients assigned to placebo over 48 weeks. The assessments in each subset are identical over the first 24 weeks. The 48-week subset will continue to provide long-term safety data in this subset of patients.

Study RPL554-CO-302 is planned as a 24-week study that will enroll 800 patients and be randomized 5:3 to ensifentrine (3 mg): placebo and is otherwise identical to the first 24 weeks of RPL554-CO-301. This study will assess population PK via sparse sampling in all patients.

Both studies will assess lung function, symptoms and quality of life over 24 weeks. Safety and tolerability will be assessed over 24 or 48 weeks.

A 3-day study was conducted where nebulized ensifentrine or placebo was administered twice daily to patients with COPD as an add-on treatment to tiotropium (Spiriva®; RPL554-CO-202). In this study, statistically significant and clinically meaningful improvements in bronchodilation were seen compared to placebo. In addition, ensifentrine significantly reduced residual lung volumes and increased the speed of onset of the bronchodilator effect to under 5 minutes.

In the first completed 4 week dose-ranging, 403-patient Phase IIb study, RPL554-CO-203, four dose levels of nebulized ensifentrine (0.75, 1.5, 3, and 6 mg) were administered twice daily to patients with moderate to severe COPD not taking additional maintenance bronchodilator therapies. All doses of ensifentrine met the primary endpoint, showing a statistically significant increase in peak FEV₁ vs placebo ($p < 0.001$) with placebo-corrected changes from baseline > 200 mL in peak FEV₁ after 4 weeks of dosing. In addition, statistically significant improvements in average FEV₁ over 12 hours were observed at all doses after the first administration, and this effect was sustained over 4 weeks. Notably, statistically significant and clinically meaningful improvements in total COPD symptoms were shown using the Evaluating Respiratory Symptoms in COPD (E-RS™: COPD) measure, a validated daily assessment of stable COPD symptoms. Ensifentrine showed a meaningful reduction in symptoms on the total score and all subscales of the E-RS at or near the minimal clinically important difference (MCID) of each.

In a second recently completed 4 week dose-ranging, 413-patient Phase IIb study, RPL554-CO-205, with ensifentrine or placebo added on to maintenance tiotropium, 4 dose levels (0.375, 0.75, 1.5, and 3 mg) of ensifentrine or placebo were administered twice daily to patients with moderate to severe COPD who remained symptomatic and with impaired lung function following a 2 week tiotropium run-in. All doses of

ensifentrine met the primary endpoint, showing a statistically significant increase in peak FEV₁ (all $p < 0.05$) which was sustained over 4 weeks. For the two highest doses, 1.5 and 3 mg, increases in peak FEV₁ were observed > 100 mL compared to placebo after 4 weeks of dosing. In addition, a statistically significant and meaningful improvement in average FEV₁ over 12 hours was shown with the 3 mg dose at Week 4 (87 mL, $p = 0.0111$). Notably, statistically significant and clinically meaningful improvements in health-related quality of life as measured by St. George's Respiratory Questionnaire (SGRQ)-COPD (Meguro, 2007) were observed at Week 4 with the 1.5 and 3 mg doses of ensifentrine added onto tiotropium (placebo-corrected; both $p < 0.05$), which exceeded the MCID for both doses.

Overall, ensifentrine was well tolerated in the 15 clinical studies conducted to date, with adverse event (AE) incidence and severity generally similar to those in the placebo-treated group. Serious adverse events (SAEs) have been uncommon and there is no apparent pattern in the SAEs reported to date.

Verona Pharma is developing nebulized ensifentrine as a maintenance therapy for patients with COPD. Information on the background of ensifentrine as described in this section can be found in the Verona Pharma plc. Ensifentrine Clinical Investigators Brochure (IB) v. 20.0, 2021 (or more current version, if applicable), unless otherwise cited.

2.3 Benefit/Risk Assessment

No significant medical risks to patients have been identified from studies conducted thus far with ensifentrine administered in the solution formulation, suspension formulation, or dry powder formulation. A slight increase in mean heart rate (up to 12 beats per minute [bpm]) without reported medical significance at a 6 mg supratherapeutic doses has been reported in healthy volunteers (RPL554-PK-101). In patients with COPD, transient increases in peak heart rate of 3 bpm vs placebo have been observed with the 6 mg twice daily dose only over 4 weeks. Otherwise, non-clinical and clinical data to date do not indicate any areas of particular medical safety concern.

Effects on reproductive performance in male rats given the highest dose of 15.5 mg/kg/day included lower number of pairings of dosed males resulting in pregnancy in undosed females, higher pre and post implantation loss resulting in lower mean litter size, and lower sperm motility and higher abnormal sperm. No ensifentrine-related adverse effects were observed at 5.75 mg/kg/day (20.5 times the maximum recommended human dose based on area under the curve [AUC]). There were no effects on embryo-fetal survival and development in either rats or rabbits in the main embryo-fetal development studies. Ensifentrine had no effects on fertility or reproductive performance in female rats.

Ensifentrine has statistically and clinically significant bronchodilator as well as anti-inflammatory effects. As such, the clinical development of ensifentrine is focused on the treatment of obstructive and inflammatory lung diseases, including COPD.

Considering the consistent improvements in lung function, symptoms, and health-related quality of life across multiple studies in patients with COPD and the overall favorable safety profile in studies to date, the benefit/risk profile of ensifentrine is considered positive.

More detailed information about the known and expected benefits and risks and reasonably expected AEs of ensifentrine can be found in the Verona Pharma plc. Ensifentrine Clinical IB v. 20.0, 2021 (or more current version, if applicable).

3.0 OBJECTIVES AND ENDPOINTS

3.1 Objectives

3.1.1 Primary Objective

The primary objective of this study is to evaluate the efficacy of ensifentrine on lung function compared to placebo over a 12-hour dosing interval in patients with moderate to severe COPD.

3.1.2 Secondary Objectives

- To evaluate the effect of ensifentrine on other lung function parameters.
- To evaluate the effect of ensifentrine on COPD symptoms.
- To evaluate the effect of ensifentrine on health-related quality of life.

3.1.3 Other Objectives

- To evaluate the effect of ensifentrine on moderate/severe COPD exacerbations.
- To evaluate the effect of ensifentrine on health utility and healthcare resource utilization (HRU).

3.1.4 Safety Objective

To evaluate the safety and tolerability of ensifentrine over 24 and 48 Weeks.

3.2 Endpoints

3.2.1 Primary Endpoint

Average forced expiratory volume in 1 second (FEV₁) area under the curve (AUC)_{0-12h} post-dose at Week 12 (change from baseline).

3.2.2 Secondary Endpoints

- Peak FEV₁ over 4 hours post-dose at Week 12 (change from baseline).
- Evaluating-Respiratory Symptoms (E-RS) Total Score at Week 24 (change from baseline as a weekly average).
- SGRQ total score at Week 24 (change from baseline).
- Morning trough FEV₁ at Week 12 (change from baseline).

- Average FEV₁ AUC_{0-4h} post-dose at Week 12 (change from baseline).
- The proportion of St. George's Respiratory Questionnaire (SGRQ) responders at Week 24.
- Rescue medication use at Week 24 (change from baseline).
- Transitional Dyspnea Index (TDI) at Week 24.
- Evening trough FEV₁ at Week 12 (change from baseline).
- Peak FEV₁, morning and evening trough FEV₁, FEV₁ AUC_{0-4h}, E-RS Total Score, SGRQ responder analysis, and TDI at other Study Visits (change from baseline).
- SGRQ total score at Weeks 6 and 12 (change from baseline).
- Rescue medication use at Weeks 6 and 12 (change from baseline).

3.2.3 Other Endpoints

- Moderate/severe COPD exacerbation frequency over 24 and 48 Weeks (this individual study and pooled with data from study RPL554-CO-302).
- Time to first moderate/severe COPD exacerbation over 24 and 48 Weeks (this individual study and pooled with data from study RPL554-CO-302).
- Study withdrawal before 24 and 48 Weeks.
- EuroQol-5-Domain Questionnaire (EQ-5D-5L) at Week 12 (change from baseline).
- Healthcare Resource Utilization (HRU) over 24 and 48 Weeks.
- Average FEV₁ AUC_{6-12h} post-dose at Week 12 (change from baseline).

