8.3.3 Health Outcomes

The schedule for all health outcomes assessments are provided in the SoA (Section 1.3).

During Study Visits

All patient reported outcomes administered during study visits should be administered at the beginning of a study visit before any physical activity or spirometry, except for Healthcare Utilization assessment, which can be done at any point during the visit. The following is the recommended order *as applicable for a given visit*:

- mMRC
- SGRQ
- EQ-5D-5L
- Baseline/Transitional Dyspnea Index (BDI)/TDI

8.3.3.1 *St. George's Respiratory Questionnaire*

The SGRQ Patient Reported Outcome (PRO) measure is designed to assess health-related quality of life in patients with COPD in terms of symptoms, daily activity limitation, and psychosocial well-being (Jones , 1991). The SGRQ is completed by the patient.

8.3.3.2 *EuroQol-5-Domain Questionnaire*

The EQ-5D-5L questionnaire is a standardized instrument designed to measure health utility in terms of mobility, self-care, usual activities, pain/discomfort, and anxiety/depression (Szende, 2014). The EQ-5D-5L questionnaire is completed by the patient.

8.3.3.3 *Baseline Dyspnea Index/Transitional Dyspnea Index*

The BDI is used to measure the severity of dyspnea in patients at baseline (Mahler, 1984). Mahler also developed the TDI which measures changes in patient dyspnea from baseline. The instruments are scored based on ratings for functional impairment, magnitude of task, and magnitude of effort. The BDI and TDI are administered by site staff via patient interview.

8.3.3.4 *Healthcare Utilization*

All unscheduled visits to a physician office, visits to urgent care, visits to emergency department, and hospitalizations for any cause and/or related to COPD will be recorded in the eCRF. In addition, visits and contacts that are due to a COPD exacerbation will be assessed at each clinic visit and recorded in the exacerbation form of the eCRF.

8.3.3.5 *Patient Perception Survey*

At the Follow-up contact, the study site will survey each patient regarding patient perception of their study treatment assignment.

At Home

8.3.3.6 *Evaluating-Respiratory Symptoms Questionnaire*

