16.3.1.4. HRU

HRU is measured by the following events: unscheduled visits to a physician office, visits to urgent care, visits to emergency department and hospitalizations for any cause and/or related to COPD and visits/contact due to COPD exacerbation. These will be recorded on the Log Form and "COPD Exacerbation" pages of the eCRF, respectively.

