Moderate/severe exacerbations occurring after the day used as offset will not be considered in the analysis. The treatment difference from the negative binomial model will be expressed as an

[REDACTED]

annualized risk ratio. The data will also be summarized by treatment group over duration of the study period. Only moderate/severe COPD exacerbations meeting the protocol-specified criteria will be presented in the listing.

Time to study medication withdrawal or study withdrawal will be presented per stratum and by the following subgroups: patients who withdrew from study medication/study before Week 24 visit and patients who withdrew from study medication/study before Week 48 visit for 48-week stratum.

Time to first moderate/severe COPD exacerbation during the study period will be presented for all patients using full study length, all patients using data truncated at week 24 visit, and patients in 48-week stratum. The primary analysis will include log-rank test stratified by region, actual background medication strata and actual smoking strata. Summary of number of patients with events and number of patients censored will be presented. Outcome will be visualized using a Kaplan-Meier plot.

The health index and VAS score for EQ-5D-5L questionnaire will be analyzed using ANCOVA approach, as described in Section 16.1.3 of the SAP, with data imputation described in Section 16.2.2.3 of the SAP.

HRU over a period truncated up to Week 24 visit for all patients (24-week and 48-week strata combined) and for 48-week stratum only will be summarized for each event and for overall count. HRU during follow-up period will not be presented.

- Sensitivity analysis or subgroup analysis may be considered following results of the patient perception survey. The survey will be summarized to investigate if there are any signs of breaching of the blind related to the appearance of study medication.
- Proportion of E-RS total score responders will be analyzed by means of a logistic regression model with fixed effects for treatment, region, actual background medication strata and actual smoking strata at baseline and baseline E-RS total score as covariate. Missing data will be imputed as described in Section 16.2.2.3 (range method).

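### The HRU overall count can include exacerbation contacts twice, and HRU gets raw counts with no time adjustment or treatment estimate

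*Protocol*

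**What the plan says.** Protocol 3.1.3 sets the objective: "To evaluate the effect of ensifentrine on health utility and healthcare resource utilization (HRU"). Protocol 3.2.3 lists the matching endpoint, "Healthcare Resource Utilization (HRU) over 24 and 48 Weeks".

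Protocol 8.3.3.4 describes two streams of collection. The first covers every unscheduled office visit, urgent care visit and emergency visit, and "hospitalizations for any cause and/or related to COPD will be recorded in the eCRF". The second is extra: "In addition, visits and contacts that are due to a COPD exacerbation will be assessed at each clinic visit" and entered on the exacerbation form.

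SAP 16.3.1.4 puts both streams into one list of HRU events. The list ends with "hospitalizations for any cause and/or related to COPD and visits/contact due to COPD exacerbation", and the sources named are the Log Form and the COPD Exacerbation page.

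SAP 16.3.3 gives the analysis. HRU up to the Week 24 visit for all patients, and HRU for the 48-week stratum, "will be summarized for each event and for overall count". Follow-up is excluded. No model, rate, offset, ratio, interval or test is named for HRU. The same section gives the exacerbation count a negative binomial model with log study time as offset, and gives EQ-5D-5L, the other half of the objective, an ANCOVA with multiple imputation.

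**The concern.** There are two separate problems.

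**Counting.** The two streams are not disjoint. Protocol 11.6.3.2 defines a severe exacerbation by the need for in-patient hospitalization, so each one is also a hospitalization for any cause. If a site follows Protocol 8.3.3.4 literally, the admission appears on both pages. If the overall count adds the pages, exacerbation contacts carry double weight. Any treatment difference that comes through exacerbations then looks larger in the total than it is.

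**Estimation.** The objective asks for an effect, but the plan gives raw counts. Raw counts under-record the arm that is observed for less time. Loss of observation may be linked to the outcome: under Protocol 11.6.7 a second or severe exacerbation leads to discontinuation of study treatment. Patients who then take one of the reduced options in Protocol 7.2.1 to 7.2.3 still have exacerbations assessed, but healthcare utilization is not on those lists. The two HRU streams can therefore cover different lengths of time in the same patient.

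**Working it through.** The documents state no HRU rate, effect size or power, so there is no planned figure to reproduce. The check is a comparison of the text followed by arithmetic on labelled assumptions.

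**Text.** Protocol 8.3.3.4 makes the first stream all-cause and the second additional. SAP 16.3.1.4 lists both as HRU events. SAP 16.3.3 asks for an overall count. No section says whether a contact on both pages counts once or twice, or whether the overall count is of contacts or of patients.

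**Effect of duplication.** Assumptions: a share *s* of placebo contacts is due to exacerbations; ensifentrine multiplies these by *r* and leaves other contacts unchanged; every exacerbation contact is on both pages; both pages are summed.

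- Each contact counted once: ratio = (1 − s) + s·r
- Exacerbation contacts counted twice: ratio = [(1 − s) + 2·s·r] / (1 + s)

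| s | r | Counted once | Counted twice |
|---|---|---|---|
| 0.2 | 0.6 | 0.8 + 0.12 = 0.92 | 1.04 / 1.2 = 0.867 |
| 0.3 | 0.6 | 0.7 + 0.18 = 0.88 | 1.06 / 1.3 = 0.815 |
| 0.5 | 0.6 | 0.5 + 0.30 = 0.80 | 1.10 / 1.5 = 0.733 |
| 0.4 | 0.8 | 0.6 + 0.32 = 0.92 | 1.24 / 1.4 = 0.886 |
| any | 1.0 | 1.00 | 1.00 |

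At s = 0.3 the apparent saving is 1 − 0.815 = 18%, against a true 12%. At s = 0.5 it is 27% against 20%. If treatment has the same effect on all contacts, both counts are inflated by the same factor and the ratio is unchanged.

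**The opposite reading.** Suppose sites enter each contact on one page only. The sum is then correct, but the Log Form holds only the non-exacerbation contacts. Its own ratio is (1 − s)/(1 − s) = 1.00 under the same assumptions, and its emergency and hospital rows omit exacerbations. A counting rule is needed on either reading.

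**Effect of unequal observation.** Let *w* be the proportion withdrawing and *t* the mean fraction of the window observed before withdrawal. Mean exposure is 1 − w(1 − t). Protocol 9.2 gives only an overall 25% withdrawal trigger, so the split by arm is assumed. For 22% on ensifentrine and 30% on placebo, the overall rate is (500 × 0.22 + 300 × 0.30)/800 = 25%. With no true effect, the crude per-patient ratio is 0.890/0.850 = 1.05 at t = 0.5 and 0.835/0.775 = 1.08 at t = 0.25. For 20% and 33% it is 1.08 to 1.13. With equal withdrawal it is 1.00.

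**The case against.** The strongest reply has four parts.

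- **Double counting is not shown.** A reader might infer that the plan does double count. The documents do not establish that. They do not say that one contact is entered on both pages or that the pages are added. SAP 16.3.1.4 assigns the two groups of events to the two pages respectively, which could mean one page per contact, and SAP 8 leaves table content to output shells that are not among the documents. This stands: double counting is a risk on the natural reading of Protocol 8.3.3.4, not a fact.
- **By-event summaries are planned too.** A reader might also infer that HRU cannot answer its objective at all. That goes too far. Summaries by event type in a randomised comparison are informative, if weak. What is missing is an estimate with its precision.
- **Exposure is partly handled.** In the 48-week stratum, allocation is 3:1, so 300 of 500 ensifentrine patients (60%) but only 100 of 300 placebo patients (33%) are followed for 48 weeks. Truncating at Week 24 for all patients and showing the 48-week stratum separately removes that imbalance. This stands, and leaves unequal withdrawal or unequal HRU collection as the remaining source of bias.
- **Nothing confirmatory depends on it.** HRU is outside the hierarchy in Protocol 9.1 and SAP 7.4, and Protocol 9.4.1 promises no HRU model. This also stands. It limits the importance of the point but does not supply a counting rule or an estimate for a stated objective.

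**Conclusion.** The concern holds in a limited form. As written, the HRU overall count can include exacerbation contacts twice. HRU is planned only as raw counts, by event and overall, with no allowance for observed time and no treatment estimate, although the objective is the effect on HRU.

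The sizes above are illustrations, because the exacerbation share, the treatment effect and the withdrawal split are all assumed. The shift from 0.88 to 0.815, or from 0.80 to 0.73, needs a 40% cut in exacerbation contacts, no effect on other contacts, and duplication of every exacerbation contact. It is smaller with partial duplication and zero if the effect is uniform. The exposure bias is zero if observed time is equal between arms. The by-event summaries and the Week 24 truncation limit the harm. The endpoint is exploratory, and no confirmatory claim, sample size or error rate is affected.

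**What to change.** **SAP 16.3.1.4.** Define the overall total as unique contacts. Reconcile Log Form and COPD Exacerbation page entries by patient, date and type where these are captured. Protocol 11.6.4 mentions onset and resolution dates of the exacerbation, and no section shows that the page holds the date of each contact. If matching is not possible, build the total from the all-cause Log Form only, after confirming that sites enter exacerbation contacts there as Protocol 8.3.3.4 implies. Show exacerbation-related contacts as a subset of the total.

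**SAP 16.3.3.** Keep the by-event summaries and state that they are by treatment group. Add contacts per patient-year by arm, with a rate ratio and 95% CI from the negative binomial model already specified for exacerbations. Use log time under HRU observation as the offset. Total time in study is unsuitable, because patients on the reduced options in Protocol 7.2.1 to 7.2.3 accrue study time without healthcare utilization being assessed. Run the model to the Week 24 visit for all patients and to Week 48 for the 48-week stratum. State the second window explicitly, because the current sentence can be read as truncating both summaries at Week 24.

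**Cost.** Some SAP wording, one reconciliation step, a derived HRU observation time and two further model runs. No new data collection is needed if the Log Form is complete or contact dates were captured.
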